The protocol, informed consent form(s), recruitment materials, and all participant materials will be submitted to the Institutional Review Board (IRB) for review and approval. Approval of both the protocol and the consent form must be obtained before any participant is enrolled. Any amendment to the protocol will require review and approval by the IRB before the changes are implemented to the study. In addition, all changes to the consent form will be IRB-approved; a determination will be made regarding whether a new consent needs to be obtained from participants who provided consent, using a previously approved consent form.]

1. PROTOCOL SUMMARY

SYNOPSIS

Title:	SIPO1-AD: A Phase II Clinical Trial for the Assessment of Safety, Tolerability, and Efficacy of Siponimod in Patients with Mild Alzheimer's Disease
Study Description:	
Alzheimer's disease (AD) is a neurodegenerative disorder with several complex neuropathologies suspected to develop sequentially but that overlap over time as symptoms progress to dementia. Thus, to be effective, future intervention strategies will likely require combination therapies or pleiotropic agents to tackle several AD molecular pathogenic pathways simultaneously. For more than a decade, our group has been exploring the repurposing of immunomodulators for AD. Recent discussions with collaborators who specialize in multiple sclerosis suggest that sphingosine-1-phosphate receptor (S1PR) modulators are strong candidates for repurposing in AD. Indeed, S1PR modulators are blood brain barrier (BBB) penetrant and display pleiotropic actions, including immunomodulation and neuroprotective properties. S1P is a versatile endogenous molecule that regulates several signaling pathways by binding to five G-protein-coupled receptors, which are expressed in high levels in cardiac, vascular, immune, and brain cells. This widespread localization of S1PR was the historical basis for Novartis Pharmaceuticals, Inc, to develop oral formulations of S1PR modulators for multiple sclerosis (MS), which proved successful and resulted in two marketed oral compounds (i.e., fingolimod and Siponimod).
 
In the present project, we intend to collaborate with Novartis to use the most recently FDA-approved S1PR modulator, Siponimod. Based on MS and animal experimentation literature, we hypothesize that Siponimod could alter the rate of neurodegeneration as measured by lowering the rate of brain atrophy in mild AD dementia subjects. In this Phase II, proof-of-concept, translational clinical study, mild AD dementia subjects will be randomized 2:1 and will receive gradual titration regimen of Siponimod starting at 0.25mg/day and increasing up to final dosage of 1 mg/day (N=70) or placebo (N=35) for 12 months. This will be followed by a 6-month washout period. Siponimod has demonstrated positive immunomodulatory and neuroprotective actions in MS patients, and because its toxicity profile is favorable for use in older individuals, Siponimod has a strong potential to alter markers of mild AD dementia pathology and disease trajectory.

Objectives:	
The primary objectives are to evaluate the safety and tolerability of the drug in subjects with mild Alzheimer's disease dementia, as assessed through regular clinical evaluations throughout the dosing period. Critically, eventual treatment-emergent toxicities will drive our decision process to pursue or stop dosing. The secondary objective is to determine drug effect on relative annual brain atrophy rates in the two groups by comparing pre- and post-exposure volumetric MRI data. Tertiary objectives will be evaluated through the utilization of cognitive assessments throughout study.
 
The study design will support two exploratory objectives using blood, CSF, and saliva biospecimen collection from subjects with mild AD dementia. Blood and CSF samples will be analyzed for AD biomarkers (amyloid beta, tau, and p-tau)

	as well as CSF inflammatory markers. Saliva samples will be assessed for amyloid-beta biomarkers (primarily Aβ40 and Aβ42), which may serve as dynamic surrogate markers of therapeutic drug efficacy.
Endpoints:	
Primary Endpoint: Safety to be evaluated through reported adverse events (AEs), clinical laboratory tests (hematology, and serum chemistry,), vital signs, physical and neurological examinations, and electrocardiograms (EKGs).
 
Secondary Endpoints: Change in rates of neurodegeneration as measured with volumetric MRI.
 
Tertiary Endpoint: Cognitive changes throughout duration of the study to be evaluated through cognitive assessments, including, ADCOMS (with ADAS-Cog13, MMSE, CDR-SOB as source measures)
 
Exploratory: ADCS-ADL + CSF/blood/saliva biomarkers

Study Population:	105 male and female outpatients, 50-85 years of age, diagnosed with early/mild Alzheimer's disease dementia primarily residing in Phoenix, AZ and greater surrounding areas. Because of the local demographics, the study population will mostly consist of Caucasians, although all efforts will be made to enroll other ethnicities.
Inclusion and Exclusion Criteria	
Inclusion Criteria
 
To be eligible for this study, subjects must meet the following inclusion criteria:
 
 1. Male or female at least 50 years of age, but less than 85 (84 at time of screening) 2. Females must be of non-childbearing potential or have negative pregnancy test at time of screening. Women of non-childbearing potential are defined as women who are either permanently sterilized (hysterectomy, bilateral oophorectomy or bilateral salpingectomy) or who are postmenopausal. Women will be considered postmenopausal if they have been amenorrheic for >12 months prior to the planned date of enrollment. 3. Must have a diagnosis of mild Alzheimer's Dementia determined by medical record review. 4. Vision and hearing must be sufficient to comply with study procedures. 5. Be able to take oral medications. 6. Must be able to attend all study visits indicated in the schedule of visits. 7. Must have a collateral informant/study partner who has significant direct contact with the patient at least 10 hours per week and who is willing to accompany the patient to specified clinic visits, supervise administration of all study medication, and be available for telephone visits/interviews. 8. Documented Mini Mental State Exam (MMSE) score between 20-26 at Screening Visit Day 1. 9. CT or MRI scan of the brain within 12 months of Screening Visit Day 1 showing no evidence of significant focal lesions or other pathology which could contribute to dementia. If neither a CT or a MRI scan is available from

the past 12 months, a scan fulfilling the requirements must be obtained before randomization.

10. Hachinski ischemic score must be ≤ 4 .
11. Geriatric depression scale must be ≤ 10 .
12. Prior to dosing all randomized study subjects must show proof they have received immunization to varicella (VZV IgG).
13. Each patient must be assessed for capacity to consent by the principal or sub-investigators in order to provide informed consent. If the patient is deemed unable to provide informed consent, they must have a legally authorized representative (LAR), and the LAR must review and sign the informed consent form. If the patient does not have a LAR, the patient must appear able to provide informed consent and must review and sign the informed consent form. If the patient is deemed unable to provide informed consent and does not have a LAR, they cannot participate in the study. In addition, the patient's study partner/informant (as defined in the study inclusion criteria) must sign the informed consent form. If the LAR and the patient's study partner/informant are the same individual, he/she should sign under both.
14. No active suicidality identified on Columbia-Suicide Severity Rating Scale (C-SSRS).
15. Patients with stable prostate cancer may be included at the discretion of the Medical Monitor.
16. Patients who are on monoclonal antibody medication for the treatment of Alzheimer's (ex. lecanemab, donanemab) for > 6 months or have discontinued monoclonal antibody medication for the treatment of Alzheimer's for > 6 months may be included if all other criteria have been met.

Exclusion Criteria

Subjects will be excluded if they have any of the conditions listed below:

1. Taking one of the following medications: Medications for treatment of cancer or other drugs that weaken the immune system (ex. Natalizumab and Rituximab), Amiodarone, Bishydroxycoumarin, Chloramphenicol, Cimetidine, Fluconazole, Fluvastatin, Miconazole, Phenylbutazone, Sulphinpyrazone, Sulphadiazine, Sulphamethizole, Sulfamethoxazole, Sulphaphenazole, Trimethoprim, and Zafirlukast.
2. Current active infection in participants including, but not limited to, herpes zoster, herpes infection, bronchitis, sinusitis, upper respiratory infection and fungal skin infection. Siponimod may increase the risk in participants with active infections.
3. If participant received mRNA COVID-19 vaccination, must have received last dose at least 3 months prior to first dose of study drug/placebo.
4. Current evidence or history within the last 3 years of a neurological or psychiatric illness that could contribute to

dementia, including (but not limited to) epilepsy, focal brain lesion, Parkinson's disease, seizure disorder, or head injury with loss of consciousness.

5. Meets DSM IV criteria for any major psychiatric disorder including psychosis, major depression and bipolar disorder.
6. Known history of or self-reported active alcohol and/ or substance abuse within the past three years.
7. Isolated living circumstances which would prohibit a study partner from providing sufficient and credible information about the participant.
8. Poorly controlled hypertension
9. Known Atrioventricular heart block, known heart block type I-III.
10. History of myocardial infarction or signs or symptoms of unstable coronary artery disease within the last year (including revascularization procedure/angioplasty).
11. Severe pulmonary disease (including chronic obstructive pulmonary disease) requiring more than 2 hospitalizations within the past year.
12. Untreated obstructive sleep apnea.
13. Any thyroid disease (unless euthyroid on treatment for at least 6 months prior to screening).
14. Active neoplastic disease (except for skin tumors other than melanoma) within five years.
15. Absolute lymphocytopenia of $<1,000/\text{mm}^3$, or a history of lymphocytopenia within the past two years.
16. Absolute neutropenia of $<1,000/\text{mm}^3$, or a history of neutropenia within the past two years.
17. History of/ or current thromboembolism (including deep venous thrombosis).
18. Any clinically significant hepatic or renal disease (including presence of Hepatitis B or C surface antigen or an elevated transaminase levels of greater than 2x the upper limit of normal (ULN) or creatinine greater than 1.5 x upper limit of normal (ULN)).
19. Clinically significant hematologic or coagulation disorder including any unexplained anemia, or a platelet count less than $100,000/\mu\text{L}$ at screening.
20. Use of any investigational drug within 30 days or within five half-lives of the investigational agent, whichever is longer.
21. Unwilling or unable to undergo CT or MRI imaging.
22. In the opinion of the investigator, participation would not be in the best interest of the subject.
23. Subjects with CYP2C9*3/*3 genotyping

*Waiver/exemption requests for Inclusion/Exclusion Criteria may be submitted to the medical monitor for review and approval on an individual basis.

Phase:

IIb

Description of Sites/Facilities Enrolling Participants:	This is a single site study located at Barrow Neurological Institute in Phoenix, Arizona.
Description of Study Intervention:	Siponimod 1 mg/day vs. placebo taken daily orally (ratio 2:1 drug: placebo). The drug escalation scale will be used starting from 0.25mg/daily ending with final dosage of 1mg/day.
Study Duration:	The trial will last 4-5 years.
Participant Duration:	Participants completing the study will be involved for up to 20 months in duration, from screening to end of study. Treatment period will be 52 weeks and 6-month washout/observation

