1.1 STUDY PROCEDURES

Visit 1, Day -56 to 0 Screening Visit (Up to 8 weeks)

During the screening visit, the subject (or their legally authorized representative as appropriate) and study partner / informant (if not the same as their LAR) will sign the informed consent document prior to undergoing any study procedures.

The following tests and evaluations are used to determine subject eligibility:

- Informed consent
- Inclusion and exclusion criteria
- *CYP2C9* genotyping (buccal swab)
- Medical History & Verify Diagnosis
- Concomitant medication reconciliation
- Serum pregnancy test if applicable
- Neurological and physical examination
- Vital signs, height and weight
- Labs (CBC, CMP, Hep B, Hep C, HIV, TSH)
- Coagulation panel (PT, PTT, INR) (optional, only for patients who opt into LP/CSF substudy)
- Cognitive assessments (MMSE, Hachinski, GDS)
- Columbia Suicide Severity Rating Scale (C-SSRS)
- MRI (MRI or CT within the past 12 months of Screening Visit Day 1)
- EKG (electrocardiogram)

Patients who do not meet the eligibility criteria will not be randomized and will be considered screen failures. Screen failures may be re-screened once per PI discretion for eligibility..

If no MRI or CT scan has been completed within the past 12 months: Participants who consent will be scheduled for volumetric MRI (vMRI) to be completed prior to the Baseline Visit.

In addition, participants will be asked to complete an ophthalmic evaluation to obtain a baseline evaluation prior to the start of treatment.

Optional Lumbar Punctures for CSF Sub-Study

For lumbar punctures, the principal investigator (or sub-investigator) will perform the procedure. A separate section will be added to the consent form, which the subject (or their legally authorized representative) will sign to authorize the lumbar puncture and collection of cerebrospinal fluid (CSF). To ensure subject safety, PT, INR, and PTT levels will be checked at baseline prior to any lumbar puncture procedure and subsequently prior to each follow-up visit where a lumbar puncture is being performed.

A follow-up telephone check will be conducted the day after each lumbar puncture within 24-48 hours. If there is persistent spinal headache, a blood patch may be administered at the discretion of the investigator.

Optional Saliva Sub-Study

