***Do not dose patient on Baseline visit if the patient opted for LP. Refer to Visit 2.5 instead**

- Inclusion/exclusion check
- Concomitant medication reconciliation
- Labs (CBC w/ diff, CMP, TSH)
- Labs (PT, PTT, INR) to be completed and reviewed pre-lumbar puncture for all lumbar punctures
- Optical Coherence Tomography (OCT) Eye Exam (must be done before dose)
- Serum pregnancy test (if applicable)
- EKG (EKG to be completed at pre- and 6-hours post-dose \pm 10 minutes)
- Vital signs including weight
- Vital signs, post-dose, every hour for 6 hours \pm 10 minutes
- Neuro and physical exam
- Cognitive assessments for data collection only (MMSE, ADAS-cog 13, CDR, ADCS-ADL)
- Volumetric MRI (+ 4 weeks window) if vMRI was not completed during Screening
- Blood biomarkers
- Randomization*
- Dispense study drug, patient dose to be completed in-clinic*
- Drug diary provided to patient*
- Drug accountability including instructions on how to take treatment drug*
- Adverse event Assessment

The following are to be completed if participants opted into one, or both, of the optional studies:

- Lumbar puncture followed by phone check in 24hrs-48 hrs post-lumbar puncture
- Saliva collection pre- treatment dose

Visit 2.5 at Day 1 of dosing, Baseline Visit, 0.25mg/day (Only for patients who undergo LP at Baseline)

- Vital signs including weight (pre-dose), hourly vital signs \pm 10 minutes (post-dose observation for 6 hours)
- EKG (pre-dose and post-dose at 6 hours \pm 10 minutes)
- Randomization
- Dispense study drug, patient dose to be completed in-clinic
- Drug diary provided to patient
- Drug accountability including instructions on how to take treatment drug
- Adverse event assessment

Every effort will be made to complete baseline visits in the morning to allow for ample time to monitor participants after the first visit. Subjects will be administered first treatment dose in clinic and will be monitored for the following 6 hours. Every hour subjects will undergo BP/HR monitoring and AE symptom check. Investigator will be notified of BP/HR each hour with HRs rate less than 55 BPM being indicative of immediate intervention by investigator.

At the 6-hour mark after first dose participant will undergo an EKG for safety monitoring. Investigators will review EKG results for bradyarrhythmia and prolonged QT interval. Review of EKG will be completed prior to participant leaving clinic for participant safety.

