1.2 SCHEDULE OF EVENTS (SOE)

The Schedule of Events is summarized in tabular form above and detailed below in table 1. All subjects will be expected to complete all evaluations in study.

Table 1: Study Schedule of Events

Study Visit	Screening Visit	0.25 mg/day		0.50 mg/day		0.75 mg/day		1 mg/day						
		Baseline Visit	Phone Visit	Visit 3	Phone Visit	Visit 4	Phone Visit	Visit 5	Phone Visit	Visit 6	Phone Visit	Visit 7	Phone Visit	Visit 8
Study Day (+/- 7 days)	-56 to 0	1	7	14	21	28	35	42	49	56	63	70	84	112
Study Week		0	1	2	3	4	5	6	7	8	9	10	12	16
Informed Consent	X													
Eligibility Criteria	X													
CYP2C9 genotyping	X													
Medical History	X	X	X	X	X	X	X	X	X	X	X	X	X	X
Concomitant Medications	X	X	X	X	X	X	X	X	X	X	X	X	X	X
Labs (CBC, CMP, TSH)	X	X		X		X		X		X		X		X
Coagulation panel (PT, PTT, INR)	X ^e	X ^e												
Serum Pregnancy Test	X ⁱ	X ⁱ												
EKG	X	X ^h		X ^h		X ^h		X ^h		X		X		X
Vital signs, Height/Weight	X ^k	X ^{mk}		X ^{mk}		X ^{mk}		X ^{mk}		X ^k		X ^k		X ^k
Neuro and Physical Exam	X	X		X		X		X		X		X		X
Cognitive Assessments	X ^a	X ^{b,c}												
Eye exam (OCT)		X ⁿ								X				
MRI (preferred) or CT scan ^g	X ^g													
Randomization		X												
Volumetric MRI		X ^o												
Blood biomarkers		X		X		X		X		X		X		X
(Optional) Saliva		X ^r												
(Optional) Lumbar Puncture ^d		X ^{d,e,r,s}												
Drug Accountability		X		X		X		X		X		X		X
Adverse Event Assessment		X	X	X	X	X	X	X	X	X	X	X	X	X
Dispense Study Drug and Drug Diary		X ^s		X		X		X		X		X	X	X

a. Screening MMSE, Hachinski, Geriatric Depression Scale (GDS), and CSSR-S

b. ADCOMS (MMSE, ADAS-Cog 13, CDR-SOB)

c. ADCS-ADL

d. All lumbar punctures will be followed by phone call 24-48hrs after lumbar puncture to ensure participant safety

e. Drawn only if opted in for LP. Results required before LP is completed schedule

f. Dispense of visit drug and first treatment to be completed in clinic

g. If not done within 12 months. Study willing to accept historical CT if done in past 12 months

h. EKG 6 hour post-dose observation. ±10 minutes

i. If participant is of child-bearing potential

k. Height will only be recorded at screening

m. Post-dose vitals every hour ±10 minutes

n. Eye exam (OCT) must be pre-dose

o. vMRI can be done within window of 4 weeks

p. End of study vMRI can be done within window of ±4 weeks

r. Optional substudy procedure if patient opts in

s. If patients opt in for LP on Baseline visit

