3.1.3 ASSESSMENT OF POTENTIAL RISKS AND BENEFITS

Given Siponimod has been FDA approved since 2019 (and its predecessor, fingolimod, was FDA approved in 2010), a significant amount of information is available from MS studies outlining the benefits and adverse events for this drug.

In this current clinical trial, our design incorporates specific strategies to enhance benefits while mitigating risks. We are selectively enrolling patients with mild AD dementia. Our approach involves initiating treatment at a conservative dose of 0.25 mg, gradually increasing to a final dose of 1.0 mg based on a predetermined titration schedule. Regular visits will include comprehensive safety assessments, encompassing procedures such as blood draws and EKGs, to diligently monitor for potential adverse events through the trial period.

+ Fetal Risk

Based on animal studies, Siponimod may cause fetal harm. For this reason, we will confirm that all female subjects are not pregnant at screening and are not of child-bearing potential (i.e. surgically sterile or LMP >12 months ago).

DRUG INTERACTIONS

In clinical trials it was noted that the following drug interactions can occur in participants. Due to this it was determined that the possible risks do not outweigh the benefits of potential treatment, and as such, the following drug classes will be deemed exclusionary.

+ Anti-Neoplastic, Immune-Modulating, or Immunosuppressive Therapies

- Siponimod has not been studied in combination with anti-neoplastic, immune-modulating, or immunosuppressive therapies. Caution should be used during concomitant administration because of the risk of additive immune effects during such therapy and in the weeks following administration.
- When switching from drugs with prolonged immune effects, the half-life and mode of action of these drugs must be considered to avoid unintended additive immunosuppressive effects.
- Because of the characteristics and duration of alemtuzumab immune suppressive effects, initiating treatment with Siponimod after alemtuzumab is not recommended.

+Anti-Arrhythmic Drugs, QT Prolonging Drugs, Drugs That May Decrease Heart Rate

- Siponimod has not been studied in patients taking QT prolonging drugs.
- Class Ia (e.g., quinidine, procainamide) and Class III (e.g., amiodarone, sotalol) anti-arrhythmic drugs have been associated with cases of Torsades de Pointes in patients with bradycardia.

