Dosing of Siponimod in AD is limited by two parameters. First, although no bradycardia was observed in a chronic high dose regimen in healthy subjects³⁸ and at therapeutic doses in MS patients undergoing a daily dose-titration regimen²⁷, these data were collected on young to middle-aged adults (age range 18-60). However, there is no literature on the possible cardiac AEs induced by Siponimod in older adults (age >60), which favors using a low dose in such individuals. Second, the *CYP2C9*2* and *CYP2C9*3* alleles are known to metabolize Siponimod more slowly than the *CYP2C9*1* genotype (half-lives of ~51 [double] and 126 hours [quintuple], respectively). *CYP2C9*2* allele is observed in 4-18% of Caucasians and Hispanics, which constitute a large proportion of the AD patients seen at BNI, and *CYP2C9*3* allele has a frequency of 2-20% in the same ethnicities, while Asians, African decedents, and Native Americans have lower frequencies for both genotypes^{33,43}. These observations of moderate frequencies for *CYP2C9*2* and *CYP2C9*3* alleles, and the recommendations from the FDA-approved package insert encourage us to administer the suggested low dose of 1 mg/day in *CYP2C9*1/x* and *CYP2C9*2/x* subjects, and to exclude *CYP2C9*3/3* subjects (0.4-0.5% of the population) for the present study. Consequently, and after discussing these issues with our MS specialty colleagues, for safety reasons we have selected to administer a maximum dose of 1 mg/day to the mild AD subjects that we will enroll in this proof-of-concept study. Further, instead of the daily titration regimen recommended in MS, we will apply a biweekly dose increment of 0.25 mg/day over the course of 6 weeks, with the first dose given at each increased strength (dose increases by 0.25 mg at a time) taken during in-person visits at BNI to monitor for any eventual AEs that could emerge with dose increases.

END OF STUDY DEFINITION

A participant is considered to have completed the study if he or she has completed all phases of the study including the last visit or the last scheduled procedure shown in the Schedule of Events (SOE).

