7. STUDY POPULATION

INCLUSION CRITERIA

See table on page 5 for *inclusion*/exclusion criteria.

EXCLUSION CRITERIA

See table on page 6 for inclusion/*exclusion* criteria.

LIFESTYLE CONSIDERATIONS

Because of its ability to inhibit CYP enzymes, study subjects will be recommended to not eat grapefruit or drink grapefruit juice.

SCREEN FAILURES

Screen failures are defined as participants who consent to participate in the clinical trial but are not subsequently randomly assigned to the study intervention or entered in the study. The collection of a minimal set of screen failure information is required to ensure transparent reporting of participants who are deemed as a screen failure, to meet the Consolidated Standards of Reporting Trials

(CONSORT) publishing requirements and to respond to queries from regulatory authorities. Minimal information includes demographics and eligibility criteria.

Because of inherent daily variations in cognitive performance observed in the clinic, if MMSE score is outside of the range 20-26 at the initial screening, the PI may request MMSE retesting after a two week period.

Patients who do not meet one or more of the entry criteria will not be randomized and will be considered screen failures. Screen failures may be re-screened once per PI discretion for eligibility.

STRATEGIES FOR RECRUITMENT AND RETENTION

The clinical trial aims to recruit a total of 105 subjects from the study site, Barrow Neurological Institute (BNI). Study goal is to achieve a balanced enrollment, targeting approximately 50% male and 50% female participants. These study subjects will be outpatients diagnosed with mild AD dementia at BNI.

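### Inclusion 2 admits fertile women on a negative pregnancy test, while sections 3.1.3 and 11 bar them because of fetal risk

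*Protocol*

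**What the plan says.** Inclusion 2 in the synopsis states "Females must be of non-childbearing potential or have negative pregnancy test at time of screening". It defines women of non-childbearing potential as "permanently sterilized (hysterectomy, bilateral oophorectomy or bilateral salpingectomy) or who are postmenopausal", the latter meaning more than 12 months without menses. Section 7 has no criteria list of its own and sends the reader back to that table ("See table on page 5 for" the inclusion criteria), so the synopsis wording is the operative rule.

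The visit schedule fits that wording. Section 1.1 lists "Serum pregnancy test if applicable" at screening and repeats the test at baseline. In the Schedule of Events (section 1.2), footnote i sets the condition for the test: "If participant is of child-bearing potential".

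Section 3.1.3, under Fetal Risk, states a different rule: "we will confirm that all female subjects are not pregnant at screening and are not of child-bearing potential". Section 11, Reporting of Pregnancy, also requires women to be surgically sterile or of non-childbearing potential, and gives suspected teratogenicity in animals as the reason. Its list of sterilizing procedures includes bilateral tubal ligation and leaves out salpingectomy; Inclusion 2 does the reverse.

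**The concern.** Inclusion 2 joins its two branches with an or, so a negative test stands in for non-childbearing potential. Sections 3.1.3 and 11 make non-childbearing potential a requirement for every woman. Both cannot govern enrolment, and site staff working from the criteria table would apply the permissive version.

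At stake is exposure of a woman who can conceive to a suspected teratogen for the 52-week treatment period, which two sections of the protocol say will not happen. The rest of the protocol is written as if no such woman were enrolled, so little would protect her if she were.

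**Working it through.** The protocol states no figure on this point to reproduce. The check sets the texts side by side and then counts visits.

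**Test case.** A woman aged 50 or over, not sterilized, with menses in the past 12 months and a negative screening test:

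| Place in protocol | Rule | Eligible? |
|---|---|---|
| Synopsis, Inclusion 2 | Non-childbearing potential, or negative test | Yes |
| Section 1.2, footnote i | Serum test where she can conceive, at screening and baseline | Consistent with yes |
| Section 3.1.3, Fetal Risk | Not pregnant and not of childbearing potential | No |
| Section 11, Reporting of Pregnancy | Surgically sterile or of non-childbearing potential | No |

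A generous reading of the or does not remove the conflict. The baseline test comes after eligibility has been confirmed, and a test for a woman who can conceive has a purpose at that point only if such women may be enrolled.

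**Cover if she is enrolled (sections 1.1 and 1.2).**

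- Pregnancy tests: screening and baseline, 2 in all. Pregnancy at first dose is therefore largely covered.
- Later dosing-period visits with routine blood draws: days 14, 28, 42, 56, 70, 112, 168, 224, 280, 336 and 364, which is 11 visits. Pregnancy tests at these visits: 0.
- Time without a scheduled test: day 364 − day 1 = 363 days.
- Contraception: asked only of male participants (section 11).
- Follow-up to the end of pregnancy: written only for a participant's partner (section 11).
- Stopping drug: none of the three circumstances in section 9 names pregnancy, although one lets the investigator or the DSMB stop treatment for medical reasons.
- A participant's own pregnancy: mentioned only as a notification duty in section 11, Adverse Event Reporting, worded for the period after the study.

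**Sterility lists.** Salpingectomy is missing from the section 11 list, but a woman who has had one still qualifies there through the non-childbearing branch. Tubal ligation is the item that changes who qualifies: section 11 accepts it, the Inclusion 2 definition does not. At present the test route lets such a woman in; once that route is deleted, a premenopausal woman with tubal ligation would be excluded unless the definition is changed too.

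**Figures for the fallback fix.**

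- Tests on existing draws: days 56, 112, 168, 224, 280 and 336 (every 56 days) plus day 364 = 7. Adding day 392 gives 8.
- Post-dose period: the Justification for Dose in section 6 gives "half-lives of ~51 [double] and 126 hours [quintuple], respectively" for the CYP2C9*2 and *3 alleles. With five half-lives as an assumed convention, 5 × 51 h = 255 h = 10.6 days and 5 × 126 h = 630 h = 26.3 days. A 28-day period covers both. Visit 14 falls 392 − 364 = 28 days after the target end of dosing.

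**The case against.** The contradiction itself is not in dispute; the counter-arguments concern its weight and the details.

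- *Rarity.* Participants are at least 50 and have mild dementia, fertile women are tested twice before dosing, and the investigator may refuse entry or stop drug. This stands as a limit on frequency. It does not settle which rule applies, and the protocol's own reason for excluding these women is possible fetal harm.
- *The missing safeguards may be deliberate.* If fertile women are meant to be excluded, it is coherent to have no female contraception, no on-treatment tests and partner-only follow-up. That is fair, and it suggests Inclusion 2 is a drafting slip. It also means the safeguards depend on an exclusion that the operative criterion does not make.
- *Other provisions apply.* Section 11 treats a congenital anomaly as a serious adverse event and requires its reporting. True, but that concerns the outcome in the offspring, and does not detect or manage a pregnancy during dosing.
- *The fallback contains choices.* The 8-week test interval and the five-half-life convention do not come from the protocol, and the 126 h half-life is a cautious upper value because *3/*3 participants are excluded. This is accepted; these figures matter only if the sponsor decides to enrol fertile women.

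**Conclusion.** The point holds. The operative inclusion criterion admits women whom sections 3.1.3 and 11 exclude, and the schedule of tests follows the permissive version. The number affected is likely very small given the lower age limit of 50, and the protocol offers no basis for an estimate. For each such woman, 2 pre-dose tests are followed by 363 days and 11 dosing-period visits with no scheduled pregnancy test. There is no effect on randomization, endpoints, power or analysis. The correction should be made because the eligibility rule conflicts with the protocol's own mitigation of fetal risk. The conclusion rests on the protocol text alone; the only outside assumption is the five-half-life convention, which supports just the post-dose period in the fallback.

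**What to change.** **Preferred.** Delete the negative-test alternative from Inclusion 2, so that non-childbearing potential is required of every woman. Keep the screening and baseline serum tests as confirmation where status is uncertain, and reword footnote i in section 1.2 to say so. In the same amendment, use one definition of non-childbearing potential in Inclusion 2, section 3.1.3 and section 11, and state whether bilateral tubal ligation counts. The simplest choice is to count it, as section 11 already does, so that the deletion does not exclude those women by accident.

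**If fertile women are meant to be eligible.** Amend sections 3.1.3 and 11 instead and add:

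- contraception for women during dosing and for 28 days after the last dose;
- a serum test at Visits 6 and 8 to 13 (about every 8 weeks) and at Visit 14;
- a rule to stop study drug on a positive test;
- follow-up of a participant's pregnancy to its end.

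**Cost.** The preferred route changes Inclusion 2 and its definition, with matching text in sections 1.2, 3.1.3 and 11. As with any amendment it needs IRB approval, and if the consent form changes, a decision on re-consent. At most it produces a few extra screen failures. The alternative adds no visits, since its 8 tests use blood draws already scheduled, but it does add the assays and contraception counselling.
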